### **6.3.14.3 Cortisol**

Pharmacodynamic biomarkers (salivary cortisol, hair cortisol and 8h urinary cortisol) will be presented in listings [Listing 16.2.6.7.1, Listing 16.2.6.7.2 and Listing 16.2.6.7.3] and summarized [Table 14.2.8.1].

The association between cortisol assessments at baseline and baseline MADRS total score will be presented in a separate scatter plots for the intent to treat population [Figure 14.2.6.3].

# Statistical Analysis Plan

Taisho Pharmaceutical R&D Inc.  
Protocol TS121-US201

Statistical Analysis Plan (SAP)

Final 2.0  
18 Dec 2018  
CONFIDENTIAL

## 6.3.15 Subgroup Analysis for Primary Endpoint

The association between MADRS total score change from baseline to Visit 6 and the following demographic or anthropometric information, baseline severity, baseline PD biomarkers or other background information will be explored using descriptive subgroup analysis of MADRS total score from baseline and scatter plots. Factors and covariates in the analysis, as well as the MADRS total score change will be presented in a listing for the intent to treat population [Listing 16.2.6.8] including any pooled groups and subgroup categories used in the analysis:

- Gender (Male, Female)
- Age
- BMI
- Race (White, Other)
- Baseline MADRS score
- HAM-D score at Visit 1.1
- Concomitant ADT (SSRI, Other)
- Age at MDD diagnosis
- MDD duration
- Baseline PD biomarkers
  - Cortisol (salivary cortisol morning and evening and the ratio of morning to evening, hair cortisol, 8h urinary cortisol)
  - Plasma copeptin
  - Inflammatory markers (IL-1, IL-6, HS-CRP, TNF-  $\alpha$ )

Subgroup categories will be determined based on clinical preference or derived from the data based on the sample median or quartiles.

Descriptive summaries by treatment will be presented of MADRS total score change from Visit 3 to Visit 6 in selected subgroup categories for the intent to treat population [Table 14.2.9.1]. The MADRS total score change will be presented in scatter plots versus subgroup categories or the underlying ungrouped covariate corresponding to tabulated subgroup categories [Figure 14.2.7.1].

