10.5.3 Pharmacodynamic (PD) Analysis

With respect to the PD outcome variables, the same MMRM/non-parametric methods as described in Section 10.5.2.1 will be used to compare the difference between the three treatment groups on the each of PD endpoint depending on the distribution of the data.

Changes from Baseline (Visit 3) to EOT (Visit 6) for the following:

- Plasma copeptin
- Inflammatory markers (IL-1, IL-6, HS-CRP, and TNF- α)

Pharmacodynamic biomarkers (salivary cortisol, hair cortisol, plasma copeptin, 8h urinary cortisol and inflammatory markers (IL-1, IL-6, HS-CRP, and TNF- α)) will be evaluated post-hoc to explore relationship of responders and non-responders to baseline characteristics. The analysis will be used to inform, potentially, on future trial design. A separate plan will document analyses of PD samples. All results, including baseline PD biomarkers (salivary cortisol, hair cortisol, plasma copeptin, 8h urinary cortisol and inflammatory markers (IL-1, IL-6, HS-CRP, and TNF- α)), will be listed with relevant metadata.

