### 2.2 Exploratory Objective

- To evaluate the effectiveness of biomarkers in predicting TS-121 response with retrospective stratification of patients via baseline values of HPA axis and inflammatory biomarkers

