# Statistical Analysis Plan

Taisho Pharmaceutical R&D Inc.  
Protocol TS121-US201

Final 2.0  
18 Dec 2018

Statistical Analysis Plan (SAP)

CONFIDENTIAL

- Figure 14.2.6.3 Baseline Montgomery-Asberg Depression Rating Scale (MADRS) Total Score versus Baseline Pharmacodynamic Biomarkers (Intent to Treat Population)
- One page each for salivary cortisol, hair cortisol and 8h urinary cortisol. Scatter plot using different symbols for TS-121 10 mg, TS-121 50 mg and Placebo treatment groups. X-axis is baseline Pharmacodynamic Biomarker (Cortisol level). Plot baseline MADRS total score.*
- Figure 14.2.7.1 Montgomery-Asberg Depression Rating Scale (MADRS) Total Score Change from Baseline versus Baseline Patient Characteristics (Intent to Treat Population)
- Refer to shells document.**
- One page per 'patient characteristic' in Listing 16.2.6.8. Scatter plot using different symbols for TS-121 10 mg, TS-121 50 mg and Placebo treatment groups. X-axis is baseline Patient Characteristic (may be group score). Plot MADRS total score change from baseline. In case of grouped scores in only 2 or 3 groups then present overlay box plots (median with 25th to 75th percentiles) of the MADRS Total score change per group and treatment.*
- Figure 14.3.1.1 Time-matched Post-Baseline Alanine Aminotransferase versus Total Bilirubin (Safety Analysis Population)
- Refer to shells document.**
- One page, two panels. Left is Placebo Group and right is Overall TS-121 Groups. Include scheduled and unscheduled post-baseline assessments. Units are  $\times$ ULN for horizontal and vertical axes and scale is logarithmic.*
- Figure 14.3.1.2 Time-matched Post-Baseline Aspartate Aminotransferase versus Total Bilirubin (Safety Analysis Population)
- As Figure 14.3.1.1.*
- Figure 14.3.2.1 Peak Post-Baseline Alanine Aminotransferase versus Peak Total Bilirubin (Safety Analysis Population)
- As Figure 14.3.1.1, one point per patient and unmatched unscheduled results are included.*
- Figure 14.3.2.2 Peak Post-Baseline Aspartate Aminotransferase versus Peak Total Bilirubin (Safety Analysis Population)
- As Figure 14.3.1.1, one point per patient and unmatched unscheduled results are included.*

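### SAP 6.3.15 shows MADRS change by marker and arm but never estimates the treatment-by-marker contrast, or its uncertainty, that the biomarker-prediction objective calls for

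*SAP*

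**What the plan says.** SAP 2.2 words the exploratory aim as follows: "To evaluate the effectiveness of biomarkers in predicting TS-121 response with retrospective stratification of patients via baseline values of HPA axis and inflammatory biomarkers". Protocol 4.5 gives its purpose, which is to identify possible screening or stratification factors for later trials.

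The analysis serving it is SAP 6.3.15, where the association between MADRS change and the baseline markers "will be explored using descriptive subgroup analysis of MADRS total score from baseline and scatter plots". The details are:

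- Table 14.2.9.1: "Descriptive summaries by treatment will be presented of MADRS total score change from Visit 3 to Visit 6 in selected subgroup categories".
- Figure 14.2.7.1 (SAP Table 3): "Scatter plot using different symbols for TS-121 10 mg, TS-121 50 mg and Placebo treatment groups. X-axis is baseline Patient Characteristic".
- Categories: "Subgroup categories will be determined based on clinical preference or derived from the data based on the sample median or quartiles".

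Protocol 10.5.3 adds that the PD biomarkers "will be evaluated post-hoc to explore relationship of responders and non-responders to baseline characteristics". It does not say whether this comparison is made within arms, over all arms pooled, or in the active arms only. The same section says: "A separate plan will document analyses of PD samples". The SAP's PD and subgroup sections do not refer to such a plan, although SAP 6.1.5 does send pharmacogenomic analysis to a separate one.

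**The concern.** A marker predicts response to TS-121 if the drug-placebo difference varies with the marker. That is a treatment-by-marker interaction. A marker related to MADRS change equally in all arms is prognostic, and selecting patients on it would not enrich a later trial for drug effect.

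The quantity that tells the two apart is the difference between arms in the marker's gradient. The SAP displays the ingredients, but leaves the contrast and its standard error to the reader. A pilot meant to inform the selection of future patients would then end with a set of plots and cell means, and no stated precision for the one comparison the objective concerns.

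**Working it through.** **1. Is the interaction estimated anywhere in the SAP?**

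| Analysis | Outcome | Baseline marker × treatment term? |
|---|---|---|
| Primary MMRM (6.3.13.1) | MADRS change | No; no biomarker in the model |
| Copeptin ANCOVA (6.3.14.1) | Copeptin change | Yes, but not on MADRS |
| Inflammatory-marker ANCOVA (6.3.14.2) | Marker change | Yes, but not on MADRS |
| PD scatter plots (6.3.14.1 to 6.3.14.3) | Baseline MADRS against baseline marker; for copeptin and inflammatory markers also MADRS change against marker change | No estimate |
| Subgroup table and plots (6.3.15) | MADRS change | Shown by arm; no estimate |

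The interaction form is already in the SAP, with a p<0.1 check for copeptin, but it is not applied to the outcome named in the objective.

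**2. Do the by-arm displays contain the information?** Yes. A simulation of 5,000 trials, with 60 patients per arm, a median split and within-cell SD 1, gave:

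| Marker | High-minus-low in the active arm | Active gradient minus placebo gradient |
|---|---|---|
| Prognostic only, 0.5 SD | -0.50 SD | 0.00 SD |
| Predictive only, 0.5 SD | -0.50 SD | -0.50 SD |

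Within the active arm the two markers look identical. Set against placebo they differ, on average.

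**3. How precise is that contrast?** The inputs are 60 per arm (Protocol Synopsis) and an assumed median split, giving 30 per cell. The documents state no SD, so results are in units of the within-cell SD of MADRS change.

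- SE for one dose versus placebo = SD × √(4/30) = 0.365 SD.
- 95% CI half-width = 1.96 × 0.365 = 0.72 SD. For an assumed SD of 8 to 12 points, this is 5.7 to 8.6 MADRS points.
- Chance that a purely prognostic marker shows an apparent interaction above 0.5 SD in either direction: 0.5/0.365 = 1.37, for which the two-sided normal tail is about 0.17. The simulation gave 16.6%.
- Both doses pooled against placebo: SE = SD × √(2/60 + 2/30) = 0.316 SD, half-width 0.62 SD.
- With an assumed 20% dropout (24 per cell): SE = SD × √(4/24) = 0.408 SD, half-width 0.80 SD.

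**4. How many contrasts will be inspected?** SAP 6.3.15 lists five cortisol measures (saliva morning, evening and their ratio; hair; urine), copeptin and four inflammatory markers: 5 + 1 + 4 = 10. With two doses there are 20 contrasts. If no marker is predictive and each is split at the median, the expected number exceeding 0.5 SD is 20 × 0.17 = 3.4. This expectation does not require the markers to be independent.

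**5. What could the estimate deliver?** For one dose, 80% power needs an interaction of 2.80 × 0.365 = 1.02 SD, and power at 0.5 SD is about 28%. The value of the addition therefore lies in the estimate and its interval. A significance test would contribute little.

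**The case against.** The strongest reply is that the plan already shows what is needed. Placebo appears in every marker category, and SAP 6.3.1 makes n, mean, SD and SE the default summary statistics. For a two-category split, a reader could subtract the four cell means and combine the four SEs by hand. The scatter plots may also use the ungrouped covariate, and a sample median or quartile does not depend on outcome. All of this stands. It rules out the stronger reading that the plan cannot separate predictive from prognostic markers. What remains is that the SAP does not carry out the step, and that hand subtraction gives neither adjustment for baseline MADRS nor a ready answer for quartiles or a continuous marker.

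Three other inferences are tempting and unsupported:

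- A reader might infer that a prognostic marker would be carried forward as predictive. The documents contain no selection rule, and Protocol 10.5.3 says only that the results may inform later design.
- A reader might calculate how often a prognostic marker would reach significance within the active arms, or across ten markers at p<0.05. SAP 6.3.15 plans no such tests and produces no p-values.
- A reader might conclude that no interaction analysis exists at all. The separate PD plan was not available, so one there cannot be excluded.

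It can also be said that this is an exploratory aim in an unpowered pilot. That limits the weight of the point. However, SAP and protocol both say the pilot's results will be used to estimate effect size, and that purpose favours an estimate with an interval.

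**Conclusion.** The point holds in limited form. In the SAP, the objective of predicting TS-121 response receives no quantified treatment-by-marker estimate on MADRS. The contrast can be judged informally from by-arm displays, but not reliably: the CI half-width is about 0.72 SD for one dose versus placebo, and about 17% of trials would show an apparent interaction above 0.5 SD for a purely prognostic marker. These figures assume a median split, 30 per cell, equal variances and no dropout; dropout makes them worse.

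The responder versus non-responder comparison in Protocol 10.5.3 would confuse the two kinds of marker if it were pooled over arms or confined to active arms. The protocol does not say which is intended, so this is an ambiguity to close and not an established error. Of the cut-point rules, clinical preference is the one left open to choice after results are seen. The improvement is inexpensive and worth making, but it does not affect the primary analysis.

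**What to change.** In SAP 6.3.15, for each baseline PD marker:

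- Fit Visit 6 MADRS change on baseline MADRS, `GROUP`, the continuous marker (log scale where skewed) and `GROUP*marker`, using all three arms.
- Report the interaction estimate with its 95% CI for each dose versus placebo, labelled hypothesis-generating.
- Fix any display cut points before unblinding, for example at the pooled median.
- Keep Table 14.2.9.1 and Figure 14.2.7.1 as illustration.
- State that the responder comparison in Protocol 10.5.3 will be made by arm with placebo alongside.
- If the separate PD plan already contains this model, a cross-reference is enough.

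The cost is one paragraph and one extra table, with no new data. The estimates will be imprecise and should be presented as such. A false-discovery-rate column across markers is optional, and debatable given that SAP 6.3.2 rules out multiplicity adjustment.

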## 6.3.16 Safety Analysis

The analysis of the safety variables will be based on the safety analysis population. Safety will be assessed based on reported adverse events, abnormal findings from physical and

# Statistical Analysis Plan

Taisho Pharmaceutical R&D Inc.  
Protocol TS121-US201

Statistical Analysis Plan (SAP)

Final 2.0  
18 Dec 2018  
CONFIDENTIAL

ophthalmological examinations, body weight, vital sign measurements, 12-lead ECGs, C- SSRS score and clinical laboratory assessment results.

## **6.3.16.1 Adverse Events**

The following AE listings will be produced:

- All AEs [Listing 16.2.7.1]
- SAEs [Listing 16.2.7.2]
- AEs leading to Study Drug Discontinuation [Listing 16.2.7.3]
- EOCSs [Listing 16.2.7.4]
- Overdose [Listing 16.2.7.5]

The following information will be included in AE listings: Subject number, age, sex and race, treatment group, verbatim term, MedDRA preferred term (PT), system organ class (SOC), SAE indicator flag, AE onset date (and time) and study day, AE end date (and time), duration (days), severity, relationship to study drug, action taken for study drug, action taken to treat, AE outcome, and treatment emergent (TEAE) flag. Adverse events with onset date on or later than date of first dose of the randomized treatment, which also meet one of the following two criteria, will be considered TEAE.

- The AE was not present prior to the first dose of study drug for the treatment period
- The AE was present prior to the first dose of study drug for the treatment period and increased in severity

Each summary tabulation of AEs will include the number and percentage of patients who experienced TEAEs grouped to treatment (TS-121 10 mg, TS-121 50 mg and placebo) and the number and percentage of all patients who experienced AEs during placebo lead-in.

The overview of AEs includes the number and percentage of patients with at least one AE, with any SAE or with an AE that led to study discontinuation [Table 14.3.1.1].

Tables of number (and percentage) of patients with AEs summarized by SOC, PT and maximum severity [Table 14.3.1.2] and by SOC, PT and relationship to investigational product [Table 14.3.1.3] will be presented by treatment group for the safety analysis population. Treatment related AEs include those that are marked as “possibly”, “probably” or “definitely related to

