# Statistical Analysis Plan

Taisho Pharmaceutical R&D Inc.  
Protocol TS121-US201

Statistical Analysis Plan (SAP)

Final 2.0  
18 Dec 2018  
CONFIDENTIAL

- Medical and/or psychiatric history (within the past 3 years)

New or existing medical or psychiatric conditions reported prior to first administration of the investigational product [from the placebo lead-in period ] will be captured as medical history, whereas any new, untoward, or worsening medical or psychiatric conditions reported after first administration of the investigational product during the placebo lead-in period will be captured as adverse events.

- Concomitant medications

All medications used during the study will be recorded. Prior ADTs other than a current SSRI/SNRI/bupropion and prohibited medications that might influence HPA axis function used within 3 months of Visit 1 will also be recorded.

- Screening laboratory test results will be recorded

- **Serology:** Hepatitis B surface antigen (HBsAg), HIV screening and serum antibodies against Hepatitis C virus (anti-HCV antibody)
- **Urine drug screen:** The following controlled substances will be tested at Visit 1 and at Visit 3: amphetamine, barbiturates, benzodiazepines, cocaine, methadone, morphine/opiates, methamphetamine, marijuana (THC), phencyclidine (PCP), and ecstasy (MDMA).
- **Pregnancy:** For all female participants, urine pregnancy samples will be tested at specified visits indicated in the Schedule of Procedures, Table 1.

All medical history will be coded using Version 19.1 of the Medical Dictionary for Regulatory Activities (MedDRA).

Concomitant medications will be coded using the World Health Organization Drug Dictionary Enhanced (WHODDE September 2016).

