## **6.1.3.1 Adverse Events**

An adverse event (AE) is defined as any untoward medical occurrence in a patient administered an investigational product, and which does not necessarily have a causal relationship to investigational product. An AE can be any unfavorable or unintended sign (including an abnormal finding), symptom, or disease. AEs include any occurrence that is new in onset or aggravated in severity or frequency from the baseline condition, or abnormal results of diagnostic procedures (including clinically significant laboratory test abnormalities). AEs also include an intentional or accidental overdose, whether or not it is associated with symptoms. An overdose is defined as ingestion of the investigational product (accidental or intentional) more than 3 capsules in the same calendar day.

AEs will be recorded after the first administration of the investigational product in the placebo lead-in period through follow-up. AEs with onset date and time (if available) after the first administration of randomized treatment will be considered treatment emergent AE (TEAE).

Any AEs with incomplete start and end dates/times will be treated as follows:

- Adverse events with unknown start and/or end times (but where the date is known) will be imputed as post-dose for events on first treatment day of placebo lead-in or randomized treatment or with a time of 00:00 for other days. The missing time will be shown blank in the listings.
- Adverse events with incomplete start day and known month will be imputed as the later of: day of first placebo lead-in dose or first randomized dose started in that month or first of the month. Missing day will be printed -- in the listings.
- Adverse events with incomplete start dates missing month and day will be considered as the later of: day of first placebo lead-in dose or first randomized dose started in that year or January 1. Missing month and day will be printed ----- in the listings.
- Adverse events with completely unknown start dates will be considered as treatment emergent for the tabulations and the missing dates will be shown as ----- in the listings.

Details of AE classification for severity (mild, moderate or severe), action taken and relationship to test drug (not related, possibly related, probably related and definitely related) are provided in Appendix C. All AEs will be coded using MedDRA Version 19.1.

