# Statistical Analysis Plan

Taisho Pharmaceutical R&D Inc.  
Protocol TS121-US201

Statistical Analysis Plan (SAP)

Final 2.0  
18 Dec 2018  
CONFIDENTIAL

study drug”. In the case of multiple occurrences of the same AEs (at the same SOC and PT level) in an individual patient, the AE with the greatest severity will be reported in Table 14.3.1.2 and the AE with the greatest relationship to study drug will be reported in Table 14.3.1.3.

Serious AEs and EOCs, if any occur, will be summarized [Table 14.3.2.1 and Table 14.3.2.2].

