# Statistical Analysis Plan

Taisho Pharmaceutical R&D Inc.  
Protocol TS121-US201

Final 2.0  
18 Dec 2018

Statistical Analysis Plan (SAP)

CONFIDENTIAL

Table 14.2.5.4.1	Multiple Imputation Method for Missing Visits Analysis of Symptoms of Depression Questionnaire (SDQ) Total Score Change from Baseline Model Summary (Intent to Treat Population)
Table 14.2.6.1	Plasma Copeptin and Change from Baseline (Exploratory PD Analysis Population)
Table 14.2.6.2	Analysis of Plasma Copeptin and Change from Baseline at Week 6 (Exploratory PD Analysis Population)
Table 14.2.7.1	Inflammatory Markers (IL-1, IL-6, HS-CRP, and TNF- $\alpha$ ) and Change from Baseline (Intent to Treat Population)
Table 14.2.7.2	Analysis of Inflammatory Markers Change from Baseline at Visit 6 (Intent to Treat Population)
Table 14.2.8.1	Pharmacodynamic Biomarkers, Cortisol in Saliva, Hair and Plasma, Observed and Change from Baseline (Intent to Treat Population)
Table 14.2.9.1	MADRS Total Score Change from Baseline by Patient Characteristic and Treatment (Intent to Treat Population)
SECTION 14.3.1:	Adverse Events
*Table 14.3.1.1	Overall Summary of Adverse Events, Treatment Emergent and with Onset During Placebo Lead-in by Treatment (Safety Analysis Population)
*Table 14.3.1.2	Summary of Adverse Events by System Organ Class, Preferred Term, Severity and Treatment (Safety Analysis Population)
Table 14.3.1.3	Summary of Treatment Emergent Adverse Events by System Organ Class, Preferred Term, Relationship to Study Drug and Treatment (Safety Analysis Population)
SECTION 14.3.2:	Deaths, Serious Adverse Events and Events of Clinical Significance
*Table 14.3.2.1	Serious Adverse Events (Safety Analysis Population)
*Table 14.3.2.2	Events of Clinical Significance (Safety Analysis Population)
SECTION 14.3.4:	Laboratory Abnormal Assessments
Table 14.3.4.1	Abnormal Clinically Significant Clinical Laboratory Values (in Conventional Units) (Safety Analysis Population)
Table 14.3.4.2	Abnormal Clinically Significant Clinical Laboratory Values (in Standard International Units) (Safety Analysis Population)
Table 14.3.4.3	Individual Patients Evaluated for Drug-Induced Serious Hepatotoxicity (Safety Analysis Population)
SECTION 14.3.5:	Laboratory Assessments
Table 14.3.5.1.1	Descriptive Statistics for Clinical Laboratory Results (Conventional Units) (Safety Analysis Population)

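### The SAP's onset condition also governs its worsening criterion, so a fully dated lead-in AE that worsens on randomized treatment is not a TEAE if it stays in one record, and SAP 6.1.3.1 and 6.3.16.1 use different tests

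*SAP*

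**What the plan says.** SAP 6.3.16.1 admits to the TEAE set "Adverse events with onset date on or later than date of first dose of the randomized treatment, which also meet one" of two criteria. The first is that the AE was absent before the first dose of the treatment period. The second is: "The AE was present prior to the first dose of study drug for the treatment period and increased in severity".

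SAP 6.1.3.1 gives another definition. AEs are recorded from the first lead-in dose onward, and those with onset date and time (where available) "after the first administration of randomized treatment will be considered treatment emergent AE (TEAE". That sentence makes no separate provision for worsening, although the AE definition in the same section includes aggravation in severity or frequency.

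The date rules are also in 6.1.3.1. A start date with the day missing is "imputed as the later of: day of first placebo lead-in dose or first randomized dose started in that month" (or the first of the month, if that is later). If only the time is missing on a first treatment day, the event is taken as post-dose. "Adverse events with completely unknown start dates will be considered as treatment emergent for the tabulations".

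In each AE summary, 6.3.16.1 counts TEAEs by randomized arm and lead-in AEs over all patients. The title of Table 14.3.1.1 reflects this: "Overall Summary of Adverse Events, Treatment Emergent and with Onset During Placebo Lead-in by Treatment".

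**The concern.** The two parts of the 6.3.16.1 definition pull against each other. Criterion 2 concerns AEs that existed before the first randomized dose, but the condition in front of it removes AEs whose onset date is before that dose. Having written criterion 2, the SAP evidently meant to count on-treatment worsening. Read literally on one record per event, it counts almost none.

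Safety and tolerability compared with placebo is a primary objective, and the TEAE tables are the adverse-event part of that comparison; Tables 14.3.1.1 and 14.3.1.2 are marked top line. If on-treatment worsening enters the arm counts only under one way of recording it, those counts depend partly on site practice and on how complete the start date is.

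**Working it through.** No figure in the plan needs reproducing. The check applies each rule to the same events.

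**Inputs.** The first randomized dose is on study Day 16, the morning after Visit 3, and lead-in dosing starts on Day 2 (Protocol 9.1 and SAP Table 1, footnote e). The illustrative AE starts on Day 10 and worsens on Day 30.

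**Rules.**
- SAP 6.3.16.1: TEAE = (onset date ≥ first randomized dose date) AND (not present before that dose OR (present before AND increased in severity)).
- SAP 6.1.3.1: TEAE = onset after the first randomized dose, using time where available.
- Single rule: TEAE = onset on or after the first randomized dose OR (onset before it AND severity increased on or after it). The rule for wholly unknown dates is kept.

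| Case | 6.3.16.1 | 6.1.3.1 | Single rule |
|---|---|---|---|
| 1. Complete date, one record, onset Day 10 | No | No | Yes |
| 2. Worsening entered as a new AE, onset Day 30 | Yes | Yes | Yes |
| 3. Start day missing, same month as first randomized dose, imputed to Day 16 | Yes | Yes | Yes |
| 4. Start date wholly unknown (separate rule) | Yes | Yes | Yes |
| 5. A different event: onset Day 16 before the dose, time recorded, one record, worsens later | Yes | No | Yes |

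In case 1, 10 ≥ 16 is false, so 6.3.16.1 fails before either criterion is read. The same holds for any complete onset date up to Day 15. With one record per event, criterion 2 can operate only for an AE that began on the first-dose date before the dose (case 5), or for one whose partial start date is imputed to that date.

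Case 5 is where the sections disagree: 6.3.16.1 compares dates, so Day 16 passes, while 6.1.3.1 uses the recorded time, which is before the dose.

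A lead-in AE that does not worsen and has a complete date is not a TEAE under any of the three rules. The single rule therefore does not bring in ordinary lead-in events.

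**Exposure window.** AEs starting on Day 2 to Day 15 are open to case 1: 15 − 2 + 1 = 14 days. If Visit 3 falls at its +3 limit (Day 18), the window is 18 − 2 + 1 = 17 days.

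**Scale of one patient.** 1/60 = 1.7 percentage points of an arm.

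**The case against.** The strongest reply is that the SAP assumes a new record at worsening. The AE listing fields in 6.3.16.1 hold an onset date, an end date and a severity, but no date of severity change, so worsening is easier to see in a later record than within one. The same section provides for repeat records: "In the case of multiple occurrences of the same AEs (at the same SOC and PT level) in an individual patient", it reports the greatest severity. Protocol 11.1.1 and SAP 6.1.3.1 both treat aggravation as an AE, so an aggravation can have its own onset and pass both tests. On that reading criterion 2 and the onset condition fit together, whereas the one-record reading leaves criterion 2 nearly empty.

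Most of this stands. It makes the loss conditional on recording practice. It does not settle what that practice is, because neither document requires a new record. SAP 6.1.1 sets a cut for worsening only at the first lead-in dose: "worsening medical or psychiatric conditions reported after first administration of the investigational product during the placebo lead-in period will be captured as adverse events". It does not say how an AE already recorded in the lead-in is handled when it worsens after randomization. The CRF and its completion instructions are not among the documents and may contain the convention.

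It is also fair that assigning unknown dates to treatment is ordinary conservative imputation. The contrast between case 1 and cases 3 and 4 shows that the outcome depends on date completeness; it is not a separate fault.

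Several on-treatment findings must be recorded as AEs in any case: a CGI-I score of 6 or 7, Class I lens events, suicidal ideation or behavior, and clinically significant ECG or laboratory findings. What remains exposed is chiefly other, non-serious worsening of lead-in AEs.

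**Conclusion.** The definition needs correcting. As written, a fully dated lead-in AE that worsens on randomized treatment and stays in one record is not a TEAE under either section, and the two sections classify case 5 differently. The first conclusion follows from the wording of 6.3.16.1 together with the onset-only test in 6.1.3.1. Whether any patient is affected depends on a recording convention that neither document states.

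The number affected cannot be derived, because the documents give no AE rates. One patient is 1.7 percentage points of a 60-patient arm, and moves the any-TEAE proportion by that amount only if the patient has no other TEAE.

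A reader might infer more than this:
- That these events disappear. They do not: they remain in Listing 16.2.7.1 and in the lead-in column.
- That the tables will understate harm from TS-121. That would need the drug to aggravate existing symptoms more than placebo does, and sites to keep single records. The documents show neither, so no direction of bias is established.

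This is a correction worth making to top-line tables that serve a primary objective. It is not evidence that the safety comparison fails.

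**What to change.** Use one TEAE definition in SAP 6.1.3.1 and 6.3.16.1: onset on or after the first randomized dose (date and time where available), OR onset before it with an increase in severity on or after it. Count such events in the randomized arm at the post-dose severity. This confines the onset condition to criterion 1 and gives the same answer in both sections for all five cases.

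For AEs already recorded, identify worsening from later records of the same SOC and PT. Where a single record spans the first randomized dose, settle it by a blinded data query before database lock. A new CRF completion instruction alone would not be enough, since this SAP is Final 2.0 of December 2018 and an instruction would not reach events already entered.

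The cost is revised wording in two SAP sections, the matching change to the TEAE flag, and one round of queries limited to single records that span the first randomized dose. The SAP already provides for revisions used in the final report to be described there with reasons.
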